#### 4.1.3. Method of assigning subjects to treatment groups

Prior to the screening visit, subjects will be contacted in writing and informed about the planned visit dates. During the screening, UGT2B17 genotype will be determined and subject will be categorized into 2 groups: PM (genotype \*2/\*2) or EM (genotype \*1/\*1 and \*1/\*2). Allocation of PM subjects to SRD part, MD part or DDI part will be decided by subject availability with 'first come first served' principle. Therefore, the allocation of PM subject is not influenced by trial personnel, but only by the subjects' temporal availability.

##### ***SRD part (For PM and EM)***

The subjects willing to participate will be recruited to dose groups according to their temporal availability. As soon as enough subjects are allocated to 1 of the 3 dose cohorts, the following subjects will be allocated to one of the other dose cohorts. Therefore, the allocation of subjects to dose cohorts is not influenced by trial personnel, but only by the subjects' temporal availability. Because the trial includes healthy subjects from a homogenous population, relevant imbalances between the dose groups are not expected.

Subjects will be assigned to treatments (active treatment or placebo) prior to the first administration of trial medication. For this purpose, the randomisation list will be provided to the trial site in advance. Numbers of the randomisation list will be allocated to subjects by the method 'first come first served'. Subjects are then assigned to treatment according to the randomisation list. Once a subject number has been assigned, it cannot be reassigned to any other subject.

The randomisation procedure is described in Section [7.6](#).

#### ***DDI part (For PM)***

There is only one treatment sequence investigated in this part, and each subject will be allocated to the same treatment sequence (R-T). Subjects will be allocated by the method 'first come first served'. Once a subject number has been assigned, it cannot be reassigned to any other subject.

All subjects may be treated in one cohort, i.e. all subjects may receive treatment on the same calendar day. In case this is not feasible (e.g. due to logistical or recruitment reasons), the group may be split into several cohorts as required. Treatment of all subjects on the same calendar day is acceptable (for safety margin to exposure reached in previous SRD trial 1405-0001 refer to Section [1.2.1](#); for discussion of trial-associated risks and safety measures see Section [1.4.1](#) and [1.4.2](#)).

#### ***MD part (For PM)***

The subjects willing to participate will be recruited to dose group according to their temporal availability. As soon as enough subjects are allocated to 1 of the 2 dose cohorts, the following subjects will be allocated to one of the other dose cohorts. Therefore, the allocation of subjects to dose cohorts is not influenced by trial personnel, but only by the subjects' temporal availability. Because the trial includes healthy subjects from a homogenous population, relevant imbalances between the dose groups are not expected.

Subjects will be assigned to treatments (active treatment or placebo) prior to the first administration of trial medication. For this purpose, the randomisation list will be provided to the trial site in advance. Numbers of the randomisation list will be allocated to subjects by the method 'first come first served'. Subjects are then assigned to treatment according to the randomisation list. Once a subject number has been assigned, it cannot be reassigned to any other subject.

The randomisation procedure is described in Section [7.6](#).

#### **4.1.4. Drug assignment and administration of doses for each subject**

The treatments to be evaluated are outlined in Tables [4.1.4: 1](#), [4.1.4: 2](#) and [4.1.4: 3](#). The number of tablets for placebo corresponds to the number of tablets in the corresponding dose level.

Proprietary confidential information © 2021 Boehringer Ingelheim International GmbH or one or more of its affiliated companies

**Table 4.1.4: 1 BI 1323495 and placebo\* treatments, tablets of SRD part for PM**

Dose group	Substance	Pharmaceutical form	BI 1323495 10 mg	BI 1323495 50 mg	Total dose of BI 1323495
1	BI 1323495	Tablet, film-coated	1	0	10 mg
2	BI 1323495	Tablet, film-coated	3	0	30 mg
3	BI 1323495	Tablet, film-coated	0	2	100 mg
1-3	Placebo*	Tablet, film-coated	identical to active treatment		--

\* Subjects receiving placebo are equally distributed across dose groups

**Table 4.1.4: 2 BI 1323495 and placebo\* treatments, tablets of SRD part for EM**

Dose group	Substance	Pharmaceutical form	BI 1323495 10 mg	BI 1323495 50 mg	Total dose of BI 1323495
1	BI 1323495	Tablet, film-coated	3	0	30 mg
2	BI 1323495	Tablet, film-coated	2	1	70 mg
3	BI 1323495	Tablet, film-coated	0	3	150 mg
1-3	Placebo*	Tablet, film-coated	identical to active treatment		--

\* Subjects receiving placebo are equally distributed across dose groups

**Table 4.1.4: 3 Dosage and treatment schedule in the DDI part**

Treatment period	Treatment	Substance	Formulation	Unit strength	Dosage	Total dose
1	R (Reference)	BI 1323495	Tablet, film-coated	10 mg	1 tablet as single dose (Day 1)	10 mg
2	T (Test)	BI 1323495	Tablet, film-coated	10 mg	1 tablet as single dose (Day 1)	10 mg
		Itraconazole	Oral solution	10 mg/mL	20 mL (200 mg) qd for 10 days (Days -3 to 7)	2000 mg

Table 4.1.4: 4 BI 1323495 and placebo treatments, tablets of MD part for PM

Dose group	Substance	Pharmaceutical form	Unit strength	Number of units per administration	Total daily dose of BI 1323495
1	BI 1323495	Tablet, film-coated	10 mg	3 tablets bid*	60 mg
1	Placebo	Tablet, film-coated	--	3 tablets bid*	--
2	BI 1323495	Tablet, film-coated	10 mg 50 mg	1 tablet each qd	60 mg
2	Placebo	Tablet, film-coated	--	1 tablet each qd	60 mg

\*On Day 11, Subjects will receive a single dose in the morning only. On all other trial days, BI 1323495 will be administered bid.

#### ***SRD part***

For BI 1323495 treatment, a standardized meal (400-500 kcal with fat contributing to ca. 150 kcal) content [[P12-10638](#)]) will be served 30 min before drug administration. The subjects must completely consume the meal prior to drug intake.

The investigator (or authorised designee) will administer the trial medication as an oral dose together with about 240 mL of water to subjects who are in a standing /sitting position. For drug administration, the so-called four-eye principle (two-person rule) should be applied. For this, one authorised employee of the trial site should witness the administration of trial medication, and – if applicable – its preparation (e.g. reconstitution), if correct dosage cannot be ensured otherwise.

During the first 4 h after drug administration, the subjects are not allowed to lie down, i.e. no declination of the upper body of more than 45 degrees from upright posture except for medical examination, or to sleep.

Subjects will be kept under close medical surveillance until 48 h after administration of BI 1323495.

#### ***DDI part***

Administration of trial medication will be performed after subjects have fasted overnight; No food is allowed within 10 h before and for at least 4 h after intake of BI 1323495.

Subjects will be advised to not consume any food within 9 h before and 1 h after itraconazole administrations. The investigator (or authorised designee) will administer the trial medication as an oral dose together with about 240 mL of water to subjects who are in a standing / sitting position. For drug administration, the so-called four-eye principle (two-person rule) should be applied. For this, one authorised employee of the trial site should

Proprietary confidential information © 2021 Boehringer Ingelheim International GmbH or one or more of its affiliated companies

witness the administration of trial medication, and – if applicable – its preparation (e.g. reconstitution), if correct dosage cannot be ensured otherwise.

During the first 4 h after drug administration, the subjects are not allowed to lie down, i.e. no declination of the upper body of more than 45 degrees from upright posture except for medical examination, or to sleep.

Subjects will be kept under close medical surveillance until 34 h after administration of BI 1323495.

### ***MD part***

The investigator (or authorised designee) will administer the trial medication as an oral dose together with about 240 mL of water to subjects who are in a standing /sitting position. For drug administration, the so-called four-eye principle (two-person rule) should be applied. For this, one authorised employee of the trial site should witness the administration of trial medication, and – if applicable – its preparation (e.g. reconstitution), if correct dosage cannot be ensured otherwise.

On first day of treatment (Day 1) and last day of treatment (Day 11), where PK profile sampling takes place, administration of BI 1323495 (Day 1, Day 11) in the morning will be performed following a standardized normal caloric meals, which is to start and be completed within 30 minutes before the scheduled dosing.

On all other treatment days and in the evening of Day 1, subjects should take the study medication with food, preferably within 30 min after a meal. On treatment days, breakfast will be provided 30 minutes prior to the morning dose administration and dinner will be provided 30 minutes prior to the evening dose administration.

Subjects should take their morning doses on all treatment days at the same time as on the first day, +/- 1 hour. The evening dose should be taken 12 hours +/-1 hour after the scheduled time of the morning dose.

Following the first administration of trial medication, subjects will stay in inhouse confinement until Day 18. During the first 4 h after drug administration, they are not allowed to lie down (i.e. no declination of the upper body of more than 45 degrees from upright posture except for medical examination), or to sleep (Only for Day 1 and Day 11 morning).

For restrictions with regard to diet see Section [4.2.2.2](#).

#### **4.1.5. Blinding and procedures for unblinding**

##### **4.1.5.1. Blinding**

### ***SRD and MD part***

SRD and MD part is designed single-blind. The treatments administered (active or placebo) will be blinded to subjects, but will be known to the investigators (outcome assessors). Only the current dose level will be known to the subjects due to the rising dose design.

Proprietary confidential information © 2021 Boehringer Ingelheim International GmbH or one or more of its affiliated companies

A single-blind design is considered acceptable because the potential bias in this type of trial seems to be low and according to trial procedures it is assured that the investigator's knowledge of the next treatment does not influence the decision to enter a subject.

All trial data will be handled open label. This means that trial functions of the sponsor are unblinded (including clinical trial manager (CTM), data manager, statistician, bioanalyst, pharmacokineticist, pharmacometrist, drug metabolism scientist as well as dedicated personnel of the trial site).

Access to the randomisation schedule will be controlled and documented by a signed confidentiality statement, which will be stored in the TMF.

#### ***DDI part***

DDI part will be handled in an open fashion throughout (that is, during the conduct, including data cleaning and preparation of the analysis). This is considered acceptable because the potential for bias seems to be low and does not outweigh practical considerations.

#### **4.1.5.2. Unblinding and breaking the code**

As this trial will be conducted single blind or open-label, subjects' treatment assignments will be known to investigators. Therefore, no emergency envelopes will be provided.

#### **4.1.6. Packaging, labelling, and re-supply**

##### **BI 1323495 tablets**

BI 1323495 tablets will be provided by BI. They will be packaged and labelled in accordance with local law and the principles of Good Manufacturing Practice.

For details of packing and the description of the label, refer to the ISF.

The telephone number of the sponsor and the name, address and telephone number of the trial site are provided in the subject information form. Examples of the labels will be available in the ISF.

##### **Itraconazole oral solution**

Itraconazole oral solution will be obtained by the clinical trial site from a public pharmacy. The drug will be dispensed out of the original, unmodified packages.

#### **4.1.7. Storage conditions**

Drug supplies will be kept in their original packaging and in a secure limited access storage area in accordance with the recommended (labelled) storage conditions. If necessary, a temperature log must be maintained to make certain that the drug supplies are stored at the correct temperature. If the storage conditions are found to be outside the specified range, the local clinical monitor (as provided in the list of contacts) is to be contacted immediately.

#### 4.1.8. Drug accountability

The investigator, or a designee, will receive the investigational drugs from the sponsor when the following requirements are fulfilled:

- Approval of the clinical trial protocol (CTP) by the Institutional Review Board (IRB)
- Availability of a signed and dated clinical trial contract between the sponsor and the investigational site
- Approval/notification from the regulatory authority, e.g. competent authority (CA)
- Availability of the *curriculum vitae* of the Principal Investigator
- Availability of a signed and dated CTP

Only authorised personnel documented in the form 'Trial Staff List' may dispense medication to trial subjects. The trial medication must be administered in the manner specified in the CTP.

The investigator, or designee, must maintain records of the product's delivery to the trial site, the inventory at the site, the use by each subject, and the disposal of unused products. These records will include dates, quantities, batch/serial numbers, expiry ('use-by') dates, and the unique code numbers assigned to the investigational medicinal product and trial subjects. The investigator, or designee, will maintain records adequately documenting that the subjects were provided the doses specified by the CTP and will reconcile all investigational medicinal products received from the sponsor. At the time of disposal of remaining trial medication, the investigator or designee must verify that no investigational medicinal product remains in the investigator's possession.

All unused trial medication will be disposed locally by the trial site upon written authorisation of the CTM. Receipt, usage, and disposal of trial medication must be documented on the appropriate forms. Account must be given for any discrepancies.

#### 4.2. OTHER TREATMENTS, EMERGENCY PROCEDURES, RESTRICTIONS

##### 4.2.1. Other treatments and emergency procedures

There are no special emergency procedures to be followed. No additional treatment is planned. However, if adverse events require treatment, the investigator can authorize symptomatic therapy. In those cases, subjects will be treated as necessary and, if required, kept under supervision at the trial site or transferred to a hospital until all results of medical evaluations are acceptable.

##### 4.2.2. Restrictions

###### 4.2.2.1. Restrictions regarding concomitant treatment

In principle, no concomitant therapy is allowed. All concomitant or rescue therapies will be recorded (including time of intake on trial days) on the appropriate pages of the CRF.

Proprietary confidential information © 2021 Boehringer Ingelheim International GmbH or one or more of its affiliated companies

Known inhibitors/inducers of CYP3A and P-gp activity, drugs with a known hepatotoxicity profile, drugs which are contraindicated to be co-administered with itraconazole (ref. [R18-2644](#)), as well as acetylsalicylic acid or other drugs that may inhibit platelet aggregation or coagulation should be avoided during the entire trial; if necessary, short term use of ibuprofen is acceptable.

#### 4.2.2.2. Restrictions on diet and lifestyle

Poppy-seeds containing foods should not be consumed starting 3 days before the first drug administration in each treatment period, in order to avoid false-positive results in the drug-screen.

While admitted to the trial site, the subjects will be instructed not to consume any foods or drinks other than those provided by the staff. Standardized meals will be served at the times indicated in the [Flow Chart](#).

Grapefruits, Seville oranges (sour or bitter oranges) and their juices, and dietary supplements and products containing St. John's wort (*Hypericum perforatum*) are not permitted from 7 days before the first administration of trial medication until after the last PK sample collected.

Alcoholic beverages are not permitted from 7 days before the first administration of trial medication until after the last PK sample collected.

Methylxanthine-containing drinks or foods (such as coffee, tea, cola, energy drinks, or chocolate) are not allowed from 10 h before until 24 h after administration of BI 1323495.

Smoking is not allowed during in-house confinement.

Excessive physical activity (such as competitive sport) should be avoided from 7 days before the first administration of trial medication until the end of trial examination.

Direct exposure to the sun or exposure to solarium radiation should be avoided during the entire trial.

#### ***SRD part***

From 1 h before trial medication intake until lunch, fluid intake is restricted to the water provided with standard meal, water administered with the drug, and an additional 240 mL of water served at 2 h and 4 h post-dose (mandatory for all subjects). From lunch until 24 h post-dose, total fluid intake is restricted to 3 L.

During the days of urine collection, total fluid intake should be at least 1.5 litres and should not exceed 3.5 litres.

#### ***DDI part***

No food is allowed within 10 h before and for at least 4 h after intake of BI 1323495. Subjects will be advised not to consume any food within 9 h before and 1 h after itraconazole administrations.

On Day 1, from 1 h before intake of BI 1323495 (Period 1) or itraconazole (Period 2), respectively, fluid intake is restricted to the water administered with the drug, water provided with standard meal, and an additional 240 mL of water at 2 h and 4 h post-dose

Proprietary confidential information © 2021 Boehringer Ingelheim International GmbH or one or more of its affiliated companies

(mandatory for all subjects). From lunch until 23 h post-dose, total fluid intake is restricted to 3 L.

***MD part***

While admitted to the trial site, the subjects are restricted from consuming any other foods or beverages than those provided by the site staff. Standardised meals will be served at the time points described in [Flow Chart](#). A standardized normal caloric breakfast (e.g., a roll with cheese or sausage, including some dietary fat) should be served and finished within 30 minutes prior to dose administration.

In the evening of Day 1 and on Days 2 to 10, drug intake should occur with food.

Breakfast will be provided 30 minutes prior to the morning dose administration and dinner will be provided 30 minutes prior to the evening dose administration.

On Days 1 and 11, from 1 h before drug intake until lunch, fluid intake is restricted to the water administered with the drug, fluid provided with food and an additional 240 mL of water served at 2 h and 4 h post-dose (mandatory for all subjects). From lunch until 24 h post-dose, total fluid intake is restricted to 3.0 litres.

During the days of urine collection, total fluid intake should be at least 1.5 litres and should not exceed 3.5 litres.

**4.3. TREATMENT COMPLIANCE**

Compliance will be assured by administration of all trial medication in the trial site under supervision of the investigating physician or a designee. The measured plasma concentrations and/or urinary excretion of trial medication will provide additional confirmation of compliance.

Subjects who are non-compliant (for instance, who do not appear for scheduled visits or violate trial restrictions) may be removed from the trial and the CRF will be completed accordingly (for further procedures, please see Section [3.3.4.1](#)).

## **5. ASSESSMENTS**

### **5.1. ASSESSMENT OF EFFICACY**

Not applicable. No efficacy endpoints will be evaluated in this trial.

### **5.2. ASSESSMENT OF SAFETY**

#### **5.2.1. Medical examination**

At screening, the medical examination will include demographics, height and body weight, smoking and alcohol history, relevant medical history and concomitant therapy, review of inclusion and exclusion criteria, review of vital signs (BP, PR), 12-lead ECG, laboratory tests, and a physical examination. After screening, at the time points indicated in the Flow chart, it will include review of vital signs, 12-lead ECG, laboratory tests, and a physical examination.

#### **5.2.2. Vital signs**

Systolic and diastolic blood pressures (BP), as well as pulse rate (PR), will be measured by a blood pressure monitor, at the times indicated in the [Flow Chart](#), after subjects have rested for at least 5 min in a supine position. All recordings should be made using the same type of blood pressure recording instrument and on the same arm, if possible.

#### **5.2.3. Safety laboratory parameters**

For the assessment of laboratory parameters, blood and urine samples will be collected by the trial site at the time points indicated in the [Flow Chart](#) after the subjects have fasted for at least 10 h, except 4 h post dosing on Day 1 of SRD part and screening. For retests, at the discretion of the investigator or designee, overnight fasting is not required. The parameters that will be determined are listed in Tables [5.2.3: 1](#) and [5.2.3: 2](#). Reference ranges will be provided in the ISF, Section [10](#).

Manual differential white blood cell count or urine sediment examinations will only be performed if there is an abnormality in the automatic blood cell count or in the urinalysis, respectively.

Table 5.2.3: 1 Routine laboratory tests

Functional lab group	BI test name [comment/abbreviation]	A 	B 	C 	D 
Haematology	Haematocrit	X	X	--	X
	Haemoglobin	X	X	--	X
	Red Blood Cell Count/Erythrocytes	X	X	--	X
	White Blood Cells/Leucocytes	X	X	--	X
	Platelet Count/Thrombocytes (quant)	X	X	--	X
Automatic WBC relative	Neutrophils/Leukocytes; Eosinophils/Leukocytes; Basophils/ Leukocytes; Monocytes/Leukocytes; Lymphocytes/Leukocytes	X	X	--	X
Automatic WBC differential	Neutrophil, absol.; Eosinophils, absol.; Basophils, absol.; Monocytes, absol.; Lymphocytes, absol.	X	X	--	X
Manual differential WBC (if automatic differential WBC is abnormal and clinically relevant in the opinion of the investigator)	Neut. Poly (segs; Neutrophils Bands; Eosinophils/Leukocytes; Basophils/ Leukocytes; Monocytes/ Leukocytes; Lymphocytes/Leukocytes;				
Coagulation	Activated Partial Thromboplastin Time	X	--	--	--
	Prothrombin time	X	--	--	--
	INR (International Normalization Ratio)	X	--	--	--
	Fibrinogen	X	X	--	--
Enzymes	AST [Aspartate transaminase] /GOT	X	X	X	--
	ALT [Alanine transaminase] /GPT	X	X	X	--
	Alkaline Phosphatase	X	X	X	--
	Gamma-Glutamyl Transferase	X	X	X	--
	Creatine Kinase [CK]	X	X	--	--
	Creatine Kinase Isoenzyme MB [only if CK is elevated and clinically relevant in the opinion of the investigator]	X	X	--	--
Hormones	Thyroid Stimulating Hormone	X	--	--	--
Substrates	Glucose (Plasma)	X	X	--	--
	Creatinine	X	X	--	--
	GFR/ CKD-EPI	X	X	--	--
	Bilirubin, Total	X	X	--	--
	Bilirubin, Direct	X	X	--	--
	Protein, Total	X	X	--	--
	C-Reactive Protein (Quant)	X	X	--	--
	Cholesterol, total	X	--	--	--
Electrolytes	Triglyceride	X	--	--	--
	Sodium	X	X	--	--
	Potassium	X	X	--	--

 A: parameters to be determined at Visit 1 and EOT

B: parameters to be determined at Visit 2 and 3 (for trial days and time points refer to [Flow Chart](#))

C: parameters to be determined at Visit 3 (for trial days and time points refer to Flow Chart)

D: parameters to be determined at Visit 2 (only for MD part)

 Microscopic examination if erythrocytes, leukocytes, nitrite or protein in urinalysis are abnormal in urine

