**MD part (30 mg bid) (cont'd)**

Visit	Day	Planned time (relative to first drug administration [h:min])	Approximate clock time of actual day [h:min]	Event and comment	Safety laboratory 	PK blood 	PK urine 	PD blood (NE activity)	12-lead ECG 	Medical examination	Vital signs 	Questioning for AEs and concomitant therapy 
7	7	143:15	08:15								x 	x 
		143:30	08:30	Breakfast								
		144:00	09:00	Drug administration 	x 							
		148:00	13:00	Lunch 							x	
		152:00	17:00	Snack								
		155:30	20:30	Dinner 							x	
		156:00	21:00	Drug administration								
8	8	167:15	08:15		x B, 12				x 	x 	x 	x 
		167:30	08:30	Breakfast								
		168:00	09:00	Drug administration 	x 							
		172:00	13:00	Lunch 							x	
		176:00	17:00	Snack								
		179:30	20:30	Dinner 							x	
		180:00	21:00	Drug administration								
9	9	191:15	08:15								x 	x 
		191:30	08:30	Breakfast								
		192:00	09:00	Drug administration 	x 							
		196:00	13:00	Lunch 							x	
		200:00	17:00	Snack								
		203:30	20:30	Dinner 							x	
		204:00	21:00	Drug administration								
10	10	215:15	08:15								x 	x 
		215:30	08:30	Breakfast								
		216:00	09:00	Drug administration 	x 							
		220:00	13:00	Lunch 							x	
		224:00	17:00	Snack								
		227:30	20:30	Dinner 							x	
		228:00	21:00	Drug administration								

MD part (30 mg bid) (cont'd)

Visit	Day	Planned time (relative to first drug administration [h:min]) Approximate clock time of actual day [h:min]	Event and comment	Safety laboratory 	PK blood, 	PK urine 	PD blood (NE activity)	12-lead ECG 	Medical examination	Vital signs 	Questioning for AEs and concomitant therapy 
11	239:00 08:00							x 	x 	x 	x 
		239:30 08:30	Breakfast								
		240:00 09:00	Last drug administration 	x B, 14	x 	▲	x 				
		240:20 09:20			x	—					
		240:40 09:40			x	—					
		241:00 10:00			x	—		x		x	
		241:30 10:30			x	—					

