- 7 At Screening visit (SCR) and EoT: ECGs recordings are performed as single ECGs. All other scheduled ECG recordings are performed as triplicate ECGs. Recording time points may be adapted based on information obtained during the trial. ECG recording will always precede all other study procedures scheduled for the same time (see Section [5.2.4](#)).
- 8 Vital signs assessments will include pulse rate, systolic and diastolic blood pressure, height and weight. Height to be measured only at SCR, weight at SCR and at Day 1 and Day 11 prior to morning dose. Axillary body temperature to be measured at Day-1.
- 9 AEs and concomitant therapies will be recorded throughout the trial whenever reported, but will be specifically asked for at the times indicated in the [Flow Chart](#) above.
- 10 Urine drug screening and alcohol breath test will be performed at screening and prior to dosing at Day 1 of Visit 2. A breath alcohol test may be repeated at any time during the trial at the discretion of an investigator or designee.
- 11 Safety laboratory to be taken and to be medically evaluated on Day -1 prior to administration of BI 1323495.
- 12 The time is approximate; the procedures are to be performed and completed within 3 h prior to drug administration. Allocation to treatment may be performed at any time following enrolment but must be completed prior to (first) drug administration.  
Only on Day 1: PD blood (NE activity): at pre-dose time point, two samples (2x5 ml) will be collected.
- 13 3 triplicate ECGs are recorded within approximately one hour. The recordings should be separated by at least 15 minutes. The 15 minutes refer to the start of the first recording within a triplicate ECG.
- 14 Samples to be taken within 15 min prior to drug administration
- 15 At Day 1 and Day 11 subjects should have a normal caloric breakfast 30 minutes before drug administration in the morning. The breakfast should be consumed within 30 minutes prior to trial drug intake in the morning. Subjects will then fast for 4 hours after intake of morning dose. At Day 11, subjects will take only a single dose of study drug in the morning.
- 16 Morning and evening dose should be taken with a 12 h time interval (e.g. 9:00 h and 21:00 h) approximately at the same time each day during the treatment phase, within a time window of +/- 1 hour.  
On days 1 to 10: subjects stay at the site and take morning and evening dose under surveillance of site staff.  

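### In both MD flow charts the Day 11 pre-dose set B sample falls 15 to 30 min after breakfast starts, although Protocol Section 5.2.3 requires a 10 h fast and exempts no MD time point

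*Protocol*

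**What the plan says.** - **Fasting rule.** Protocol Section 5.2.3 applies to all safety laboratory blood and urine: samples are collected "after the subjects have fasted for at least 10 h, except 4 h post dosing on Day 1 of SRD part and screening". Retests are also released from overnight fasting. The same section lists set D as specific to the MD part, but the exception sentence names no MD time point.
- **Day 11 draw.** In the 30 mg bid and the 60 mg qd charts, set B sits on the 240:00 (09:00) row labelled "Last drug administration" and carries footnote 14: "Samples to be taken within 15 min prior to drug administration".
- **Day 11 meal.** Both charts place breakfast at 239:30 (08:30). Footnote 15 says "At Day 1 and Day 11 subjects should have a normal caloric breakfast 30 minutes before drug administration in the morning" and "The breakfast should be consumed within 30 minutes prior to trial drug intake in the morning". Section 4.1.4 (MD part) agrees: "administration of BI 1323495 (Day 1, Day 11) in the morning will be performed following a standardized normal caloric meals".
- **Other on-treatment pre-dose set B draws.** Days 2, 5 and 8 carry footnote 12, under which "the procedures are to be performed and completed within 3 h prior to drug administration".
- **Baseline.** Set B is drawn on Day -1 at 17:00 (footnote 11: "Safety laboratory to be taken and to be medically evaluated on Day -1 prior to administration of BI 1323495"). The Day 1 pre-dose sample is set C only, which is AST, ALT, alkaline phosphatase and GGT. SAP Section 6.7 takes the last value before BI 1323495 as baseline.
- **Analysis.** SAP Section 7.8.2 tabulates laboratory values over time and differences from baseline by planned time point, plus a reference-range table from baseline to the last on-treatment value. It makes no distinction between fed and fasted samples.

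**The concern.** The chart and Section 5.2.3 give the site incompatible instructions for the same tube. Day 11 is the steady-state profile day, and its set B is the last set B sample before the final dose. Set B contains plasma glucose. If the chart is followed, a post-meal glucose enters the Day 11 row of the by-time-point table next to on-treatment rows that can be fasted, and part of the tabulated change from baseline may come from breakfast. If Section 5.2.3 is followed instead, every Day 11 set B draw departs from footnote 14. Either choice produces a systematic deviation in a part where all subjects are in-house and the timing is fully under the site's control.

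**Working it through.** No power or precision calculation is involved. The check is clock arithmetic on the two MD charts, which agree on these rows.

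Formula: time since food = planned draw time minus start of the last charted meal, compared with the required 10 h.

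| MD draw | Draw time (h) | Last charted meal start (h) | Time since food |
|---|---|---|---|
| Set B, Day 2 | 23:30 row, before that row's breakfast | 11:30 | 12 h |
| Set B, Day 5 | 95:30 row, before that row's breakfast | 83:30 | 12 h |
| Set B, Day 8 | 167:15 | 155:30 | 11.75 h |
| **Set B, Day 11** | **239:45 to 240:00** | **239:30** | **0.25 to 0.5 h** |
| Set D, Days 1 and 11, 2 h after the morning dose | 2:00 and 242:00 | -0:30 and 239:30 | 2.5 h |
| Set D, Days 1 and 11, 12 h after the morning dose | 12:00 and 252:00 | 11:30 and 251:30 | 0.5 h |

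On Days 2 and 5 the draw shares its row with breakfast, and Section 6.1 puts the meal last. On Day 8 the draw has its own row, 15 min before the 167:30 breakfast. Day 13 (288:00) has no breakfast charted before it, so the chart creates no conflict there. Day -1 at 17:00 has no meal charted either; Section 5.2.3 would mean no food since 07:00.

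**Can any other text reconcile Day 11?**

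- Meal-last rule (Section 6.1 and the chart footnotes): it covers actions at the same time point. Breakfast (239:30) and the draw (240:00) are on different rows.
- Laboratory tolerance of ±30 min (Section 6.1): 240:00 minus 0:30 = 239:30. The earliest permitted draw coincides with the start of breakfast and is already outside the 15 min window of footnote 14.
- Retest clause (Section 5.2.3): it does not reach a scheduled sample.

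**Extent.** Subjects: 2 groups × 12 = 24 (18 active, 6 placebo). Set B draws in the MD treatment period: Days -1, 2, 5, 8, 11 and 13, so 1 of 6 is affected. Triglyceride and total cholesterol are in set A only, so glucose is the plainly meal-sensitive analyte.

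**Which tables are touched.** The on-treatment phase ends at the last dose plus 7 days: 240 + 7 × 24 = 408 h. The last set B chemistry inside that window is Day 13 (288 h), so the baseline-to-last-value table would normally use Day 13. Day 11 enters the by-time-point values and differences.

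**Feasibility of a fasted draw.** Day 10 dinner starts at 227:30. A draw on the 239:00 (08:00) row gives 239:00 minus 227:30 = 11.5 h, which meets the rule.

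**The case against.** The strongest reply is that the exception list in Section 5.2.3 was simply not extended to the MD part, and that one added sentence cures it. The set D draws at 2 h and 12 h break the same sentence, which supports this diagnosis, and a post-breakfast pre-dose haematology sample has a purpose: Section 5.4.1 normalises NE activity by a time-matched neutrophil count. That part stands, and it is why the fix has to include the exception list. An exemption alone, however, would leave glucose post-meal on Day 11 and fasted on Days 2, 5 and 8, with nothing in the tables to show it.

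A reader might infer more than the documents support:

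- *The steady-state chemistry as a whole is post-meal.* It is not. Days 5 and 8 are drawn under repeated dosing and can be fasted.
- *Day 11 is made non-comparable with baseline across set B.* No text shows that bilirubin, creatinine or the enzymes move with a meal. For glucose the baseline is Day -1 at 17:00, so a time-of-day difference exists for every morning draw and would remain after the fix.
- *The meal will pass for a drug effect because there are only 3 placebo subjects per group.* Placebo subjects eat the same breakfast and are drawn in the same window, so the meal effect is common to both arms. Each subject's Day 8 value is a further check.

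The analysis is also descriptive, clinical significance is left to the investigator, and no primary or secondary endpoint uses these values directly.

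**Conclusion.** The contradiction is real and present in both MD charts: 15 to 30 min since the start of breakfast against at least 10 h required, for all 24 planned MD subjects, at one of six set B draws. A site cannot comply with both rules. The consequence is narrow: the Day 11 by-time-point values and changes from baseline for meal-sensitive set B analytes, chiefly glucose. The documents give no figure for the size of that shift, and none is assumed here. The finding does not undermine the other on-treatment chemistry or the safety conclusions of the MD part, but it should be corrected because doing so costs almost nothing.

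This rests on three assumptions: the site follows the charted clock times; Days 2 and 5 are drawn before the breakfast on the same row; and the laboratory tables use the on-treatment phase that SAP Table 6.1: 1 defines for adverse events.

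**What to change.** 1. In both MD charts, move the Day 11 set B chemistry to the 239:00 (08:00) row with footnote 12, to be completed before the 08:30 breakfast. Fibrinogen and urinalysis, the rest of set B apart from haematology, can go with it.
2. Keep the Day 11 haematology tube on the 240:00 row with footnote 14, so that the neutrophil count stays time-matched to the pre-dose NE sample.
3. Add the MD haematology draws that remain non-fasted to the exceptions in Section 5.2.3: Day 11 pre-dose, and set D at 2 h and 12 h after the morning dose on Days 1 and 11. Without this step the charts would still conflict with the section.

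If data have already been collected under the current charts, label the Day 11 set B values as non-fasted in the laboratory tables.

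The cost is one cell and footnote per MD chart and one sentence in Section 5.2.3. The Day 11 tubes are split over two draws up to an hour apart in subjects who are already in-house. No extra assay is needed.
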